^{25, 26}. CD8 regulatory/suppressor cell function is slightly reduced in stable MS, very low during attacks and progression, and rebounds during recovery ²⁵. The defect is localized to the CD8+CD28- population ^{22, 27, 28}, a better marker than FOXP3 in this subpopulation ²⁶. We have found that CD8+CD28-Treg cells are very low in therapy-naive MS compared to healthy controls. Some MS immune modulators can elevate numbers of this subpopulation, and thus enhance anti-inflammatory functions and reduce inflammatory Th1/Th17 functions (Figure 1 below) ²⁹.

Figure 1. CD8 regulatory cell expression (CD8+CD28- T cells, arrows) is subnormal in MS (second panel) compared to healthy controls (first panel), however this low expression can be up-regulated with immune modulator (third panel).

We also illustrate our capabilities for measuring gene expression (Figure 2) and serum

yet still had markedly suppressed RNA expression for 5,000 differentially-expressed genes compared to therapy-naïve exacerbations in right panel. x-axis = fold down (to L) or up (to R); y-axis = significance

Figure 3. Multiplex analysis of proteins expressed by activated MNC. Cells were exposed to media only or to an agent that affects MS exacerbations and progression, then activated for 48 hours. Supernatants were analyzed for Th1, Th17, Th2, IFN-stimulated genes, and adhesion molecules (shown here), in addition to monokines, B cell factors, and neuroprotective proteins (dns). Columns are different patient and control groups, row are heat maps of average expression. Red = increased expression vs. media control; Blue = decreased expression vs. control; hue = statistical significance, with more saturation having lower p values (more zeros).

2.2 The hypothesis is that ACTHAR treatment in MS relapses generates a tolerogenic immune environment that suppresses inflammation and facilitates brain repair. We've found that CD8+CD28- suppressor cells are low in MS and are upregulated by several classes of immune modulators. The tolerogenic immune environment will be assessed in 18 ACTHAR-treated MS patients.

2.3 Overall objective is to determine Treg expression and neuroprotection signature, as well as identify gene and immune protein signatures in ACTH-treated MS:

2.4 Specific aims and experiment design with serum, MNC, and RNA samples from baseline, last day of ACTHAR (day 10 of therapy), 1 month post 1st dose, and months 3 and 6:

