- 1. **Aim1**. Determine immune subset expression in CD4+FOXP3 Tregs and CD8+CD28- T suppressor cells by flow cytometry at each visit above.
- 2. **Aim 2**. Determine global gene expression profiling in MNC with 913,000 probes at each visit above. Bioinformatics will include pathway analysis and ACTHAR-induced RNA signature.
- 3. **Aim 3**. Determine serum protein profiling for immune-regulated cytokines (Th1, Th2, Th17, monokines...) and neuroprotective proteins (NGF, BDNF, ACTH, HGF, CNTF, IL-10...) at each visit above.

4. **Aim 4.** All data from protein and gene expression, as well as immune subset expression will be compared to our database generated from therapy-naïve stable and exacerbating MS. ACTHAR signature will analyzed based on these comparisons.

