2.5 Methods

Blood is drawn from 18 MS patients at baseline, last day of ACTHAR (day 10 of therapy), 1 month post 1st dose, and months 3 and 6. Mononuclear cells (MNCs) from four 8cc heparin green-top tubes (40-60 million cells) are separated on Ficoll-Paque gradients. 30M cells are needed for flow cytometry. 20M cells are needed for total RNA preparation.

Specific Aim 1. Determination of ACTHAR effects on immune cell subsets in relapsing remitting MS (RRMS), emphasizing expression on CD8 cells including the CD8+CD28-regulatory subset. Flow cytometry will be conducted to determine the effect of ACTHAR on in vivo expression of surface markers on T cells (CD4, CD8, CD28, FOXP3). Reagents are from e-Biosciences and B-D. (MAbs = CD4, CD8, CD28, CD27, CD25, FOXP3).

Specific Aim 2. Global gene expression profiling in MNC will be measured with 913,000 probes at each sample. Bioinformatics will include pathway analysis and ACTHAR-induced RNA signature. Total RNA will be isolated from 20M cells, as the template for synthesizing cDNA for gene expression array analysis with Affy HTA kit. RT-PCR will be performed for validation of specific gene signatures.

Specific Aim 3. Serum from each sample will be applied on Procarta multiplex assay plates according to manufacturer's instruction. Immune, neuroprotection, and other proteins will be measured with 40 highly-selected targeted antibodies for Th1, Th2, Th17, monocyte, neuroprotection, cell proliferation and death, and adhesion molecule panels.

Specific Aim 4. Advanced bioinformatics with Gene Set Variation Analysis:

- 1. Identify differential gene expression (DEG) between groups;
- 2. Analyze pathways by Ingenuity Pathway Analysis (IPA);
- 3. Discover transcriptional signature of genes and gene pathways;

4. Build a predictive model using machine learning algorithms including Random Forests (RFs) and Support Vector Machines (SVMs).

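### Aim 4 bases the ACTHAR signature on comparison with a therapy-naive database, but trial patients may be on DMTs and no analysis use of the DMT records is stated

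*Combined protocol and SAP*

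**What the plan says.** Section 2.4, Aim 4, states that all protein, gene expression and immune subset data "will be compared to our database generated from therapy-naïve stable and exacerbating MS". It continues: "ACTHAR signature will analyzed based on these comparisons".

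Section 2.5, Specific Aim 4, lists the steps. They include "Identify differential gene expression (DEG) between groups", with the groups not defined, and "Build a predictive model using machine learning algorithms including Random Forests (RFs) and Support Vector Machines (SVMs"), with the class labels not stated.

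On DMTs, section 3.3 keeps patients on their current therapy during the relapse, places the continue-or-switch decision after the month 1 scan and blood draw, and has all DMTs recorded. The exclusion list in 3.1b names recent steroids as the only prior treatment that bars entry. Nothing requires patients to be therapy-naive. Section 3.4 plans a mixed effects model for longitudinal data and names no covariates.

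Two further places bear on the point. Aim 2 lists an RNA signature induced by ACTHAR, measured at every visit, without reference to the database. The sampling schedule in 2.4 includes a pre-dose baseline, day 10, and months 1, 3 and 6.

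**The concern.** The two sides of the Aim 4 comparison can differ in DMT use as well as in ACTHAR. The database patients are untreated, while an unknown share of the 18 trial patients carries a DMT effect in every sample, including the one taken before the first dose. A post-dose contrast with the database cannot tell the two apart.

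The protocol's own rationale suggests which way the error would run for one central marker. Section 2.2 says that "CD8+CD28- suppressor cells are low in MS and are upregulated by several classes of immune modulators", and 2.1 says: "Some MS immune modulators can elevate numbers of this subpopulation, and thus enhance anti-inflammatory functions and reduce inflammatory Th1/Th17 functions". A DMT of that kind would push the result towards the tolerogenic hypothesis. The text says some modulators do this, so it need not hold for every DMT.

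At stake is what the signature means. Section 2.6 puts forward CD8+CD28- counts, serum proteins and RNA as possible biomarkers of efficacy, so a DMT effect labelled as ACTHAR could carry into later work.

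**Working it through.** The plan gives no effect size, SD, power or database size for this comparison, so there is no figure to reproduce. The calculation below shows only what is possible.

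**Inputs.** From the documents: 18 trial patients (2.2, 3.1a) and significance level 0.05 (3.4). Assumed: two-sided test, database size N = 20 or 50, share f of trial patients on a DMT, a shift of d SD in every DMT user, true ACTHAR effect zero, patients otherwise exchangeable.

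**Step 1: bias in the database contrast.** The trial mean moves by f × d and the trial variance becomes 1 + f(1 − f)d². Then SE = √{[1 + f(1 − f)d²]/18 + 1/N}.

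Example with f = 0.5, d = 0.5, N = 50: shift 0.25; variance 1 + 0.25 × 0.25 = 1.0625; SE = √(0.0590 + 0.0200) = 0.281; ratio 0.25/0.281 = 0.89. The chance of p < 0.05 is Φ(−1.96 + 0.89) + Φ(−1.96 − 0.89) ≈ 0.14. Simulating 40,000 trials with a pooled t-test gives 0.148. Simulated rates for d = 0.2 / 0.5 / 1.0:

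| Share on a DMT | N = 20 | N = 50 |
|---|---|---|
| 0 | 0.05 | 0.05 |
| 25% | 0.054 / 0.065 / 0.111 | 0.055 / 0.076 / 0.150 |
| 50% | 0.061 / 0.115 / 0.296 | 0.064 / 0.148 / 0.420 |
| 80% | 0.079 / 0.220 / 0.634 | 0.088 / 0.304 / 0.793 |

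A larger database does not help: it makes the same offset easier to detect.

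**Step 2: if only half of the DMT users take a DMT that acts on the marker.** The effective share halves. At d = 1.0, 80% use becomes f = 0.4 and the rate falls from 63–79% to about 20–30%. At 50% use, f = 0.25 and it falls from 30–42% to 11–15%.

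**Step 3: within-patient change.** A DMT effect that is the same before and after the dose cancels. With a stable 1.0 SD shift in 50% or 80% of patients, and within-patient correlation ρ of 0.4 or 0.8, a paired test on 18 patients rejects in 4.8% to 5.1% of trials.

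**Step 4: what the change does not remove.** Section 2.1 says CD8 suppressor function is "very low during attacks and progression, and rebounds during recovery". With an assumed natural rebound of 0.25 / 0.5 SD, zero ACTHAR effect and SD of change √[2(1 − ρ)], the paired test is significant in 15% / 45% of trials at ρ = 0.4, 20% / 61% at 0.6 and 35% / 88% at 0.8. The contrast with the exacerbating database carries that rebound as well: 12–15% / 33–44% with no DMT use, and 32–43% / 60–75% with half on a DMT and d = 0.5.

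**Step 5: after month 1.** If 25–50% of patients switch DMT and the switch shifts the marker by 0.5–1.0 SD, a baseline-to-month-3 change is falsely significant in 7.5% to 70% of trials (ρ 0.4 to 0.8). Cancellation therefore holds only up to month 1.

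**Step 6: precision.** The 95% CI half-width of the baseline-versus-database offset is t × √(1/18 + 1/N): 2.03 × 0.325 = 0.66 SD for N = 20, and 2.00 × 0.275 = 0.55 SD for N = 50. The change contrast is noisier than the database contrast when 2(1 − ρ) > 1 + 18/N, that is ρ < 0.05 (N = 20) or ρ < 0.32 (N = 50).

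**The case against.** The strongest reply is that the plan already holds what is needed. Section 3.3 records DMTs and leaves the switch decision until after the month 1 samples, so DMT use should be largely stable across baseline, day 10 and month 1. Aim 2 lists an ACTHAR RNA signature from the serial samples, and 3.4 assigns a mixed model to longitudinal data. All of this stands. A reader might infer that DMTs are ignored altogether, or that the database is the only route to a signature; the documents support neither. What remains is narrower: no section makes change from baseline the basis of the signature, and Aim 4 expressly ties it to the database.

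A second reply is that every quantity driving the size is assumed and that the simulation is generous, since it shifts all DMT users equally. This also stands. At 0.2 SD the rates are 5% to 9%, close to nominal.

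A third is that change from baseline exchanges one confounder for another. In part it does: at ρ = 0.8 a 0.5 SD rebound is flagged in 88% of trials, more often than the 60–75% for rebound plus DMT use against the exacerbating database. But that database contrast contains the rebound too, so moving to within-patient change removes one source of error and adds no new one. It does not isolate ACTHAR.

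Finally, the immune work is exploratory, and no sample size or efficacy decision rests on it. That limits the urgency but does not repair the contrast.

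**Conclusion.** The concern holds for Aim 4 as written. Its stated contrast can label a DMT difference as an ACTHAR effect, and for CD8+CD28- cells some DMTs would move it in the hypothesised direction. This is a flaw in the chosen comparison and not only missing detail, and it should be corrected.

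The gap in the text is certain; the size is not. With half of patients on a DMT, the false-positive rate per marker is about 6% to 42% under the assumptions in the working, and lower if only some DMTs act on the marker. With no DMT use it is 5%.

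A reader might conclude that any signature found will be a DMT artefact. The documents do not support that: they do not say how many patients are on a DMT, and the pre-dose baseline allows a contrast free of the stable DMT part. Nor does a corrected contrast prove an ACTHAR effect, because all 18 patients receive ACTHAR while recovering from a relapse.

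**What to change.** Reword Aim 4 in 2.4 and its methods in 2.5 along these lines:

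- The signature is based on within-patient change from the pre-dose baseline to day 10 and to month 1, estimated with the mixed model in 3.4. Differential expression groups for the signature are visits of the same patients.
- Database comparisons are supporting. The pre-dose baseline versus database difference is shown with a 95% CI, to display the offset present before any ACTHAR. Post-dose comparisons are shown by recorded DMT status.
- DMT switches are flagged at months 3 and 6. Month 1 results are shown with and without patients given additional treatment under 3.2.
- If Random Forests or SVMs are used for the ACTHAR signature, the labels are baseline versus day 10 (or month 1) samples, with all samples of a patient in the same fold. A model trained on trial-versus-database labels is not evidence of an ACTHAR effect.
- Change from baseline removes only the stable DMT part and does not separate ACTHAR from natural recovery.

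**Cost.** No new visit, sample or assay is needed: the samples, DMT records and mixed model are already planned. The text of Aim 4 changes, and tables by DMT status are added.

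**Downsides.** The DMT-free subset may be small: about 14, 9 or 4 of 18 at 25%, 50% or 80% DMT use. Four patients against 20 to 50 would detect only about 1.5 to 1.6 SD with 80% power. The baseline offset is imprecise (±0.55 to 0.66 SD), so a non-significant offset does not show that DMTs have no effect. The change contrast is noisier than the database contrast if within-patient correlation is below about 0.05 to 0.32.

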2.5 Methods

Blood is drawn from 18 MS patients at baseline, last day of ACTHAR (day 10 of therapy), 1 month post 1st dose, and months 3 and 6. Mononuclear cells (MNCs) from four 8cc heparin green-top tubes (40-60 million cells) are separated on Ficoll-Paque gradients. 30M cells are needed for flow cytometry. 20M cells are needed for total RNA preparation.

Specific Aim 1. Determination of ACTHAR effects on immune cell subsets in relapsing remitting MS (RRMS), emphasizing expression on CD8 cells including the CD8+CD28-regulatory subset. Flow cytometry will be conducted to determine the effect of ACTHAR on in vivo expression of surface markers on T cells (CD4, CD8, CD28, FOXP3). Reagents are from e-Biosciences and B-D. (MAbs = CD4, CD8, CD28, CD27, CD25, FOXP3).

Specific Aim 2. Global gene expression profiling in MNC will be measured with 913,000 probes at each sample. Bioinformatics will include pathway analysis and ACTHAR-induced RNA signature. Total RNA will be isolated from 20M cells, as the template for synthesizing cDNA for gene expression array analysis with Affy HTA kit. RT-PCR will be performed for validation of specific gene signatures.

Specific Aim 3. Serum from each sample will be applied on Procarta multiplex assay plates according to manufacturer's instruction. Immune, neuroprotection, and other proteins will be measured with 40 highly-selected targeted antibodies for Th1, Th2, Th17, monocyte, neuroprotection, cell proliferation and death, and adhesion molecule panels.

Specific Aim 4. Advanced bioinformatics with Gene Set Variation Analysis:

- 1. Identify differential gene expression (DEG) between groups;
- 2. Analyze pathways by Ingenuity Pathway Analysis (IPA);
- 3. Discover transcriptional signature of genes and gene pathways;

4. Build a predictive model using machine learning algorithms including Random Forests (RFs) and Support Vector Machines (SVMs).

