3.8 Ethical considerations

The Investigators will ensure that this study is conducted in full conformance with the principles of the "Declaration of Helsinki" (last amendment October 2000, with additional footnotes added 2002 and 2004).

All patients will sign the informed consent form for the study. The Consent Forms will be signed and dated by the patient. The clinical records for each patient will document the informed consent process and that written informed consent was obtained prior to participation in the study. The Consent Forms will be revised whenever there are changes to study procedures or when new information becomes available that may affect the willingness of the patient to participate. Patients will be re-consented to the most current version of the Consent Forms (or to a significant new information/findings addendum in accordance with applicable laws and IRB policy) during their participation in the study. For any updated or revised Consent Forms, the clinical records for each patient will document the informed consent process and that written informed consent was obtained using the updated/revised Consent Forms for continued participation in the study. A copy of each signed Consent Form will be provided to the patient. All signed and dated Consent Forms will remain in each patient's study file and be available for verification by study monitors at any time.

The Principal Investigator is responsible for providing written summaries of the status of the study to the IRB annually or more frequently in accordance with the requirements, policies, and procedures established by the IRB.

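### Does a stated yield of 40-60 million cells against a combined need of 50 million leave the flow cytometry and RNA assays without a workable plan?

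*Combined protocol and SAP*

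**What the plan says.** Section 2.5 describes the cell material for each blood draw: "Mononuclear cells (MNCs) from four 8cc heparin green-top tubes (40-60 million cells) are separated on Ficoll-Paque gradients". It then gives the inputs: "30M cells are needed for flow cytometry. 20M cells are needed for total RNA preparation". The RNA figure is repeated under Specific Aim 2 in the same section: "Total RNA will be isolated from 20M cells".

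Section 2.4 asks for both assays at all five draws. Aim 1 reads "Determine immune subset expression in CD4+FOXP3 Tregs and CD8+CD28- T suppressor cells by flow cytometry at each visit above" and Aim 2 reads "Determine global gene expression profiling in MNC with 913,000 probes at each visit above". Aim 4 then uses both kinds of data: "All data from protein and gene expression, as well as immune subset expression will be compared to our database".

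The document gives no order of priority between the assays, no minimum input, and no spare tube or redraw. Section 3.4 (statistics) and section 3.7 (data management) do not take up the point. The analysis population in section 3.1a is defined by MRI time-points only.

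**The concern.** The inputs follow directly on the yield and are worded as needs. Their sum lies inside the yield range rather than at or below its lower end, so on the plan's own figures some samples may not serve both assays in full. Because both are wanted at every visit, the problem cannot be avoided by alternating them.

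Without a rule, the laboratory could decide sample by sample which assay runs on fewer cells. If yield changed with visit or treatment, reduced-input or missing results could cluster at certain visits and distort the within-patient course, or the Aim 4 comparison with the investigators' existing database. With 18 patients there is little data to spare. Section 2.6 also names CD8+CD28- cell numbers and RNA as possible efficacy biomarkers, and both come from this one pool of cells.

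**Working it through.** **Inputs, all from section 2.5:** yield from four 8 cc tubes, 40 to 60 million; flow cytometry, 30 million; RNA, 20 million; 18 patients with five draws each. The plan states no combined total, so there is no figure of its own to reproduce.

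**Combined need.** 30 + 20 = 50 million. The midpoint of the yield range is (40 + 60)/2 = 50 million.

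**Margin.** Low end: 40 − 50 = −10 million, which is 10/50 = 20% of the need. High end: 60 − 50 = +10 million. Each assay alone (30 or 20 million) is covered even at 40 million.

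**Worst case, a 40 million sample:**

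| Order | First assay | Left for the second | Share of its stated input |
|---|---|---|---|
| Flow first | 30 million | 40 − 30 = 10 million for RNA | 10/20 = 50% |
| RNA first | 20 million | 40 − 20 = 20 million for flow | 20/30 = 67% |

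**How many samples.** Planned samples: 18 × 5 = 90. No distribution of yields is given, so the number below 50 million cannot be derived; the logical bounds are 0 and 90. Under assumed shortfall rates:

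- 10%: 0.10 × 90 = 9 samples
- 25%: 0.25 × 90 = 22.5, about 22 samples
- 50%, which would follow if yields were spread evenly over the range: 0.50 × 90 = 45 samples

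These count samples below the combined stated input. They do not count lost results, because the document gives one working input per assay and no threshold below which an assay fails.

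**A fifth tube.** By proportion, each tube gives 40/4 = 10 to 60/4 = 15 million, so five give 50 to 75 million. The low end then meets the need exactly, with nothing over. The cost is 8 mL × 5 visits = 40 mL per patient. Consent may also be affected, since section 3.8 says "The Consent Forms will be revised whenever there are changes to study procedures".

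**The case for a change.** The best case for acting is that the remedy is almost free: one sentence on allocation and one log field for yield and input. Samples handled inconsistently cannot be repaired later. If half the samples fell short, independently of each other (both assumptions), the expected number of patients with full input to both assays at all five draws would be 18 × 0.5^5 = 0.56. Even at a 10% rate it would be 18 × 0.9^5 = 10.6. Section 2.5 says the cells are needed, and nothing promises that shortfalls will be handled uniformly.

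The sum and the silence on allocation both stand. The step from a low count to a worse result does not. The calculation above counts samples with full input, and no figure in the document shows that a sample on two-thirds or half of the stated input is unusable. The bias argument needs yield to vary with visit or treatment, which the document neither states nor implies. Where a result is missing, the mixed effects regression in section 3.4 can still use that patient's other visits. This protects precision but would not remove bias if the missingness were informative.

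An allocation order and a yield log are sound practice, but they belong naturally in a laboratory manual, and their absence here does not show that none exists. Nor does the document point clearly to one order. Sections 2.2 and 2.5 stress the CD8+CD28- subset measured by flow, so a rule serving RNA first would put the whole shortfall on the assay the rationale emphasises. Serving flow first leaves RNA with the proportionally larger cut. That choice is best left to the investigators, who know how each assay performs.

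**Conclusion.** No change to the plan is called for. The figures are consistent: a need of 50 million lies within a yield of 40 to 60 million, so this is an operational gap and not an arithmetic error. Its size is at most 10 million cells per affected sample, 20% of the combined need. It is confined to Aims 1 and 2 and to the part of Aim 4 that draws on them. The serum assay, the MRI outcomes and the safety data do not depend on this cell pool.

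The gap is one that a laboratory fills sensibly, by fixing an order and noting the counts. The only real design change on offer, a fifth tube, trades 40 mL of blood per patient and possible re-consent for a benefit that cannot be quantified, and it leaves no reserve at the low end.

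This conclusion takes 40 to 60 million as the usable total from the four tubes, which is the natural reading of the sentence. It also rests on there being no evidence in the document that yield depends on visit or treatment, or that either assay fails at a lower input. Evidence of either kind would strengthen the case for a written rule.

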2.6 Outcomes

This data may lead to better understanding of the mechanism of action of ACTHAR and identifying signatures/biomarkers in ACTHAR-treated MS. In addition, MRI, CD8+CD28- cell numbers, serum proteins, and RNA may be biomarkers for efficacy.

Part III. Patient criteria and publications

3.1a Inclusion Criteria

This study will be restricted to adult patients (>18 years) undergoing a clinical relapse who also must have a contrast-enhancing CNS lesion, either clinically or non-clinically relevant. Sample size under consideration is 18 patients. The population on which analyses will be conducted consists of all patients who have received at least 1 dose of study medication and for whom at least two time-points (baseline and at least one additional time-point) for MRI data are available (Intent-to-treat analysis).

3.1b Exclusion Criteria

1-Patients will be excluded if they only have a clinical relapse which is not associated with MRI findings of a new or enlarging MS lesion.

2-Patient will be excluded if they cannot give written consent

3-Patients will be excluded if they have an active infection

4-Patients will be excluded if they already received steroids (IV or oral) within last 30 days of receiving ACTHAR

5-Pregnant or lactating patients will be excluded from this study.

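### The Aim 1 antibody list has no T-lineage marker and no gate is stated, so the CD8+CD28- T suppressor count cannot be shown to exclude NK cells

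*Combined protocol and SAP*

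**What the plan says.** Section 2.4, Aim 1, states the measure: "Determine immune subset expression in CD4+FOXP3 Tregs and CD8+CD28- T suppressor cells by flow cytometry at each visit above". The draws are baseline, day 10, 1 month after the first dose, and months 3 and 6.

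Section 2.5 gives the starting material: "Mononuclear cells (MNCs) from four 8cc heparin green-top tubes (40-60 million cells) are separated on Ficoll-Paque gradients". Under Specific Aim 1 it says the markers are to be read on T cells, "emphasizing expression on CD8 cells including the CD8+CD28-regulatory subset", and it names the reagents: "MAbs = CD4, CD8, CD28, CD27, CD25, FOXP3".

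The subset carries weight in Part II. Section 2.2 supports its hypothesis with the statement that "CD8+CD28- suppressor cells are low in MS and are upregulated by several classes of immune modulators". Section 2.6 says that "MRI, CD8+CD28- cell numbers, serum proteins, and RNA may be biomarkers for efficacy". Aim 4 compares the immune subset data with the investigators' database of therapy-naïve stable and exacerbating MS.

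**The concern.** The measure is defined as a T-cell population, but the listed reagents do not establish that the counted cells are T cells. Mononuclear cells from a Ficoll gradient include NK cells. As general immunology, not stated in the documents, part of the NK population carries CD8 at low density and NK cells generally lack CD28. Of the CD8 subsets, the CD28-negative one is therefore where they would fall.

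The trial has one treated group, so no concurrent control would cancel a shift in NK cells between visits. Patients may receive IV methylprednisolone (section 3.2) and may change disease modifying therapy after month 1 (section 3.3), so the composition of the blood need not stay constant over the draws. If NK numbers moved while the T-cell subset did not, the result could be reported as a change in suppressor T cells. In Aim 4, a difference in gating between trial and database samples would add a bias unrelated to treatment.

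**Working it through.** **Step 1: reagents against definition.** The measure needs three properties: T lineage, CD8 positive, CD28 negative. The CD8 and CD28 antibodies supply the second and third. The other four (CD4, CD27, CD25, FOXP3) do not establish T lineage among CD8+CD28- events. CD3, a T-cell receptor antibody, CD56 and CD16 appear nowhere in the documents. Neither does a CD8-bright gate, a lineage exclusion or an enrichment step.

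**Step 2: a mixture model.** The plan gives no cell fractions, SD or effect size for this measure, so there is no stated figure to reproduce. Let T be the true CD8+CD28- T-cell share, N the NK share, and f the fraction of NK cells that fall in the gate.

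- Gate count: G = T + f × N
- NK share of the gate: s = f × N / G
- If N changes by x% with T fixed, G changes by s × x%

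**Step 3: no CD8-bright gating.** Assumptions, none from the documents: N 5-15% of lymphocytes, f 30-50%, T 5-10%.

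- Lowest: 0.30 × 5 = 1.5; s = 1.5 / (10 + 1.5) = 13%. Halving N lowers the count by 0.5 × 13.0% = 6.5%, about 7%.
- Highest: 0.50 × 15 = 7.5; s = 7.5 / (5 + 7.5) = 60%. Halving N lowers the count by 30%.

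**Step 4: a CD8-bright gate that still admits 10% of NK cells.** Assumptions: f = 10%, N 5-15% and T 4-12% of mononuclear cells.

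- Lowest: 0.5 / (12 + 0.5) = 4%. A 50% change in N moves the count by 2%.
- Highest: 1.5 / (4 + 1.5) = 27%. A 50% change in N moves the count by 14%.

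This grid uses a wider range for T than step 3. On the same wider range with f at 30-50%, the share is 1.5/13.5 = 11% to 7.5/11.5 = 65%, and the shift 6% to 33%.

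**Step 5: with a T-lineage marker.** f = 0, so the NK share is 0% and a change in NK cells alone moves the count by 0%.

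**Step 6: if NK cells do not move.** The absolute within-patient change is then unaffected, but the relative change is multiplied by (1 - s). A true 20% rise would appear as 0.87 × 20% = 17.4% at s = 13%, and as 0.40 × 20% = 8% at s = 60%.

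**Step 7: scale against 18 patients.** Without an SD, a percentage shift cannot be turned into an error rate. For orientation only: in a paired t test with n = 18 at 0.05, taken as two-sided because section 3.4 does not say, a shift of 0.5 SD of the paired change would be declared significant about 52% of the time.

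**The case against.** The strongest reply is that an antibody list does not fix a gate. The listed CD8 antibody already allows a CD8-bright gate with no added reagent, and the text and the caption of Figure 1 make clear that T cells are meant. The laboratory may gate this way as routine. A reader might infer that the assay as planned certainly counts NK cells. The documents do not support that: no gate is written down, so the supportable statement is that exclusion cannot be shown. An unwritten CD8-bright gate would reduce the problem, as step 4 shows. It would not give identification by lineage, and the plan would still need to state it.

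A reader might also infer that ACTHAR changes NK numbers. The documents never mention NK cells, and the 50% change used above is an illustration. A false signal needs NK cells to move; stable contamination only dilutes relative change (step 6).

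Finally, one might take this subset for a primary endpoint. It is the stated emphasis of Aim 1, but the only outcome called primary is the MRI outcome in section 1.3. Section 2.6 says only that the cell numbers may be a biomarker. Part II also rests on gene expression and serum proteins, which this point does not touch.

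What stands is the mismatch between the named population and the named reagents.

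**Conclusion.** The concern holds in this limited form. Stained as listed, and with no gate stated, the CD8+CD28- subset cannot be shown to exclude CD8-dim, CD28-negative NK cells, and a change in NK numbers over the serial draws could be read as a T-cell effect.

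On the assumptions above, the NK share is 13-60% without CD8-bright gating, with a fall of about 7-30% in the count if NK cells halve. With a CD8-bright gate admitting about 10% of NK cells, the figures are about 4-27% and 2-14%. These ranges describe what the assay could not rule out. They do not estimate what will happen in this trial. The point affects the interpretation of the emphasised Aim 1 subset and its use in Aim 4; it does not affect the MRI results. It should be corrected because the remedy is cheap and the ambiguity cannot be resolved from the listed markers afterwards.

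**What to change.** - Add anti-CD3 to the Aim 1 tube. Define the subset in sections 2.4 and 2.5 as CD3+CD8+CD28-, with the gate written out, for the within-patient analysis.
- For samples already stained without CD3, apply a CD8-bright gate and report the result as a sensitivity analysis.
- For the Aim 4 comparison, apply the same gate on both sides. If the database was stained without CD3, use CD8-bright CD28- for trial and database samples alike. If the database files cannot be re-gated, state this as a limitation of the comparison.

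The cost is one antibody and one cytometer channel, with its compensation, for each new sample, plus possible re-gating of database samples. The marker goes into the existing tube, so no extra blood or visit is needed. The documents do not say how the database was stained or whether its raw files remain, so the effort on that side cannot be sized from them. If some trial samples have already been stained without CD3, the serial data will mix two definitions, and the common CD8-bright gate is what lets them be compared.
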